Protocol 07C0111

IRB approval date 2/11/2007

**A Pilot Study of Markers of Tumor Burden and Radiation Toxicity in
the Blood, Urine, and Stool of Patients Receiving Radiotherapy for
Gastrointestinal Malignancies**

Principal Investigator: [name].¹

Study Chairperson: [name].²

Associate Investigators: [name].¹
[name], MS¹
[name], RN³
[name], RN³
[name], RN¹
[name].²
[name].²
[name].²
[name], PhD⁵
[name].⁴
[name].⁶
[name].⁶
[name], B.S., CRTP⁷
✓ [name].⁸
[name], MD⁴
[name], MD⁴

¹Radiation Oncology Branch, CCR, NCI
[name]
[name]
[name]
[contact]
[contact]

²Surgery Branch, Center for Cancer Research, NCI

³Department of Nursing and Patient Care Services, CC, NIH

⁴Medical Oncology Branch, CCR, NCI

⁵Cancer Therapeutics Branch, CCR, NCI, NIH

⁶Department of Diagnostic Radiology, CC, NIH

⁷Clinical Research Training Program, Office of the Director, NIH

⁸Laboratory of Pathology, CCR, NCI, NIH

PRECIS

Background:

- Gastrointestinal (GI) carcinomas represent one of the most commonly diagnosed malignancies in the United States¹.
- A sensitive and specific marker of tumor persistence or recurrence would permit a more accurate determination of the appropriateness of adjuvant therapy in patients with no clinical evidence of disease following curative resection and allow the diagnosis of recurrences at earlier stages that may be amenable to curative salvage therapies.
- A biomarker detectable shortly after treatment or in the early stages of chronic radiation toxicity may allow the identification of patients at risk and early intervention.

Objectives:

- Our primary objective is to determine if patient specific tumor markers in stool, urine, or serum can be reliably detected prior to treatment and followed after treatment to monitor the extent of residual disease.
- A second objective is to evaluate the predictive value of potential markers of chronic gastrointestinal injury after radiotherapy.

Eligibility

- Age \geq 18 years
- Histologically confirmed carcinoma of the gastrointestinal tract (esophagus, stomach, pancreas, rectum)
- Planned to receive radiotherapy to the site of the gastrointestinal malignancy on an NCI protocol

Design:

- This protocol provides a means of acquiring tissue, serum, urine, and stool samples from patients who will receive radiation therapy as part of their treatment for gastrointestinal malignancies.
- Patients treated with radiation therapy on NCI treatment protocols will be asked to provide samples prior to any local or systemic therapy as well as before, during and after their radiation treatment.
- These samples will be tested for the presence of tumor specific DNA mutations and aberrant methylation patterns determined to be present in each patient's tumor by screening of initial biopsy or surgical material.
- Tumor markers specific to each patient, such as tumor specific DNA mutations or aberrant DNA methylation, may provide an individualized method to evaluate disease status and determine prognosis after therapy. Additionally, a number of stool and serum markers will be explored as early indicators of acute and eventual chronic gastrointestinal injury in patients receiving radiotherapy to the abdomen.

Table of Contents

1. Introduction	
1.1 Study Objectives.....	4
1.2 Background and Rationale.....	4
2. Eligibility Assessment and Enrollment.....	9

1.0 INTRODUCTION

1.1 STUDY OBJECTIVES

1.1.1 Primary Objectives:

- To determine if tumor specific DNA mutations and aberrant DNA methylation found in the tumor of patients treated with definitive intent for gastrointestinal malignancies can be detected in the serum, urine, or stool at the time of diagnosis
- To determine if changes in mutational status at follow-up are associated with disease persistence, recurrence, or survival.
- To determine if pre-treatment, post-treatment, and follow-up measurements of TGF β 1 in the urine and plasma can be used to predict late gastrointestinal toxicity.

1.1.2 Secondary Objectives:

- To determine which biological fluid (serum, urine, or stool) is most highly associated with the detection of tumor specific DNA mutations and tumor specific DNA methylation.
- To determine which biological fluid (serum, urine, or stool) provides the best source of tumor specific DNA to measure at follow-up for association with disease persistence, recurrence, or survival.
- To determine if novel serum, urine, and stool biomarkers obtained at the time of treatment and shortly after treatment can be used to predict the likelihood of chronic gastrointestinal toxicity in patients receiving radiotherapy for gastrointestinal malignancies.
- To determine whether novel serum, urine, and stool markers obtained at the time of treatment and shortly after treatment are influenced by the radiation dose delivered to abdominal organs.

1.2 BACKGROUND AND RATIONALE

1.2.1 Gastrointestinal carcinoma

Gastrointestinal (GI) carcinomas represent one of the most commonly diagnosed malignancies in the United States¹. Although significant improvements in local control and survival have been achieved in these disease sites over the past several years, locoregional and distant failure remain a significant concern. Radiation plays a prominent role in the definitive management of many GI malignancies, including esophageal cancer, gastric cancer, rectal cancer, and pancreatic cancer. Radiation and chemotherapy are often delivered as adjuvant therapy following resection, as neoadjuvant therapy prior to resection, or as definitive therapy for these malignancies.

Assessment of response to therapy and accurate determination of disease status in gastrointestinal malignancies are complicated by the internal location of the tumors, the resolution of current imaging modalities, and the anatomic distortion introduced with surgery and radiation. When radiation is used as a component of definitive therapy, residual scarring and radiographic abnormalities often persist, making the determination of clinical response difficult. In the case of radiation as a component

of adjuvant therapy after a total resection, treatment is delivered to patients at high risk of local recurrence, often without evidence that residual disease exists. A sensitive and specific marker of tumor persistence or recurrence would permit a more accurate determination of the appropriateness of adjuvant therapy in patients with no clinical evidence of disease following curative resection and allow the diagnosis of recurrences at earlier stages that may be amenable to curative salvage therapies.

Multiple serum markers of malignancy have been explored in the hopes of developing effective screening, assessing response to therapy, and developing prognostic markers. The best studied and clinically useful tumor markers are proteins elaborated in elevated amounts by the tumor tissue, such as Ca 19-9, CEA, AFP, beta-HCG, CA 125, and PSA²⁻⁴. None of these markers is completely specific to tumor tissue, and elevation in the serum levels of these markers may be associated with inflammatory states and other benign disease processes^{3,5-9}.

1.2.2 Tumor derived nucleic acids

1.2.2.1 Nucleic acids as a tumor marker

While numerous serum, tissue, and biological fluid markers of cancer have been described, many of these markers are not specific to tumor cells. For example, proteins elaborated by tumor cells may be present in patients with no evidence of disease and in patients with non-cancerous diseases, leading to significant overlap in marker levels between healthy patients, patients with cancer, and patients with benign diseases. An optimal marker would be produced only in tumor cells, detectable with minimally invasive methods, and detectable in patients with a small burden of disease. The use of tumor nucleic acids as a marker is a promising method as tumors are typically associated with genetic mutations that are not present in the host cells. Additionally, the clonal nature of tumors supports the hypothesis that these mutations would be evident in all or most of the tumor cells if the screened mutation was an early event in tumorigenesis.

Tumor specific DNA mutations, promoter hyper- and hypo-methylation, and microsatellite alterations have been detected in the serum and biological fluids of patients with a variety of malignancies¹⁰ including non-small cell lung cancer^{11,12}, gastric cancer^{13,14}, bladder cancer^{15,16}, cervical cancer¹⁷, renal cancer¹⁸, and breast cancer¹⁹. While many studies have confirmed the ability to detect tumor DNA in patients with known malignancy and have correlated retreatment characteristics to prognosis²⁰⁻²², few have evaluated the utility of serial evaluations of these markers following therapy as a marker of disease status^{19,23}.

Other biological specimens have also been evaluated for the presence of tumor specific mutations, most successfully with stool. The development of colon cancer is associated with a stepwise progression from pre-malignant to invasive tumors which is correlated with sequential DNA mutations in the colon cells destined to become malignant²⁴. This stepwise progression through well-described mutations has been exploited in the search for a marker of colon cancer. Numerous reports in recent years have validated the detection of these genetic alterations in stool from shed luminal cells as a method to screen for both

malignant and pre-malignant lesions of the colon²⁵⁻²⁷. Other GI malignancies are potentially amenable to the approach of stool screening for DNA mutations as malignant cells are shed into the lumen and incorporated into the feces.

1.2.2.2 Circulating and excreted nucleic acids as a marker of disease status

Previous studies of DNA mutations and hyper- and hypo-methylation have screened for a variety of markers in the serum or urine of patients, however most have limited the analysis to a few markers in each study, resulting in a significant percentage of patients in whom none of the screened markers were detected. By screening the patient's tumor for mutations and aberrant methylation prior to treatment, it may be possible to select appropriate markers to monitor for each patient. This individualized approach of following markers known to be present may provide a sensitive tumor marker panel specific to each patient's tumor.

In protocol, we hope to evaluate whether we can reliably detect tumor specific mutations and tumor specific epigenetic alterations in the serum, urine, and stool of patients with GI cancers. In addition, we hope to determine if any of these biological specimens is superior for this purpose. Finally we hope to determine if the ability to detect these markers in the biological fluids of patients who have undergone curative therapy for cancer is predictive of failure.

The specific mutations and alterations in nucleic acids to be tested will vary with the primary site and histology of the tumor, based on published frequencies of mutations and aberrantly methylated sequences specific to each histology and tumor site (See Appendix IIA). Each of these mutations has been tested with positive and negative control cell lines in the laboratory of [name] and have previously undergone primer and buffer optimization (Figure 1).

The ability to recover these mutations and aberrations from paraffin embedded tumor sections has also been demonstrated in [name] laboratory. Positive and negative controls have been identified and tested for each of these mutations and methylation patterns (see Appendix IIB). Additional candidate mutations and aberrant DNA methylation markers may be tested in the tumors and specimens of patients in whom none of these are found to be present.

[figure not shown]

Figure 1. PCR products of positive and negative control cell lines and paraffin embedded tissue sections. BxPC3 is a pancreatic cell line known to have wild type ras. MiaPaCa-2 is a cell line known to have the KRM2 k-ras mutation. AsPC1 is a pancreatic cell line known to have the KRM3 k-ras mutation. CFPAC is a pancreatic cell line known to have the KRM4 k-ras mutation.

1.2.3 *Gastrointestinal Radiation Injury*

Radiation induced acute and chronic gastrointestinal toxicity is an important cause of morbidity following irradiation for malignancies of the abdomen and pelvis including gastrointestinal, genitourinary, and gynecologic cancers²⁸. Delayed radiation enteropathy presents in most patients between 6 months and 3 years after radiation^{29, 30}. A significant proportion of patients develop some form of late radiation intestinal injury that is likely underreported. Estimates in the frequency of radiation toxicity after abdominal radiation vary depending on the dose of radiation used, the location being treated, and the use of surgery and concurrent chemotherapies, however prior studies have estimated some level of intestinal dysfunction in 60-90% of patients followed longitudinally³⁰⁻³².

The small bowel, colon, gastric wall, and the rectum are frequently considered dose-limiting structures due to their lower radiation tolerance compared to surrounding organs. Long-term complications following radiotherapy can manifest as radiation enteropathy, fistulae, fibrosis, adhesions, perforations, and telangiectasias with hemorrhage^{29, 33, 34}. While several factors place patients at increased risk of gastrointestinal toxicity, such as inflammatory bowel disease or prior abdominal or pelvic surgeries³⁵, it is difficult to predict which patients are destined to experience significant morbidity.

1.2.3.1 Clinical measures of acute and chronic gastrointestinal radiation injury

Radiation induced gastrointestinal toxicity can be effectively measured with toxicity scoring schemas. Acute gastrointestinal toxicity from radiotherapy manifests differently from chronic toxicity. The RTOG and EORTC have developed toxicity scoring schemas which are widely used as the gold standard for quantifying gastrointestinal toxicity in randomized trials designed by the RTOG including those designed to test the toxicity of various treatment regimens. These toxicity scoring schemas will be used as the standard for determining GI toxicity for the purposes of this study (Appendix IIIA and Appendix IIIB).

1.2.3.2 Markers of radiation-induced gastrointestinal toxicity in serum, plasma, urine, and stool

While clinical markers provide a measure of acute and chronic radiation toxicity, there is little ability to predict which patients may eventually experience chronic radiation toxicity. The ability to identify patients shortly after treatment destined to experience radiation toxicity may eventually allow early intervention. As the biologic events responsible for chronic radiation toxicity have become better understood, it has become clear that chronic radiation toxicity is a dynamic process that develops over the course of months to years after treatment. Many key processes in this ongoing injury are being defined, and agents are being developed with the intent of mitigating ongoing damage. Development of a biomarker that could accurately predict the likelihood of eventual radiation toxicity would allow selection of patients at high risk of toxicity for trials of these agents and provide candidate biomarkers of response to preventative therapy.

Several mechanisms of this ongoing injury in normal tissues have been described from evaluation of preclinical models. Depletion of stem cells in the bowel wall with resulting denudation has been implicated in acute intestinal injury, and it was long thought that late radiation toxicity of the bowel was a result of progressive damage as a consequence of this stem cell depletion³⁴. Recently, inflammatory cytokines have been implicated in bowel and other tissues as possible mediators of chronic inflammation and fibrosis following radiation³⁶. In addition, the expression of numerous collagens and matrix remodeling peptides have been shown to be altered early in preclinical models of late GI injury³⁷⁻³⁹ and in the affected tissues of patients with late GI radiation toxicity⁴⁰. It is possible that early detection of this ongoing inflammation and pro-fibrotic pathways may eventually allow early intervention to mitigate late toxicity.

Table 1: Candidate markers of toxicity to be evaluated on this protocol

Plasma	Serum	Urine	Stool
TGFβ1	Neutrophil elastase	TGFβ1	Neutrophil elastase
	Procollagen peptides	Procollagen peptides	Calprotectin
		Intestinal permeability	pH

- TGF β 1

Cytokines are known to play an important role in the acute and chronic phases of radiation injury in a variety of organs. One of the best studied cytokines in both pre-clinical and clinical studies of chronic radiation fibrosis is TGF β 1. TGF β 1 plays important roles in cell growth, apoptosis, immune responses, and the homeostasis of the extracellular matrix (reviewed in ⁴¹). As all of these processes are implicated in radiation induced chronic intestinal injury, TGF β 1 is a candidate marker for ongoing gastrointestinal injury. In preclinical models of radiation enteropathy, TGF- β overexpression has been observed acutely and chronically in intestinal tissues^{42, 43}. This overexpression was found to correlate with fibrosis and inflammatory cell infiltrates^{42, 44, 45}.

TGF β 1 as a marker of fibrosis and chronic injury has successfully been measured in the plasma of patients treated with radiation for lung cancer. In these studies, the kinetics of TGF β 1 levels correlated with radiation induced pneumonitis⁴⁶⁻⁴⁸. Since the expression of TGF β 1 in intestinal tissues is correlated with radiation injury, it may be possible to detect the molecule as a marker of ongoing intestinal inflammation. We hope to evaluate the ability to detect this marker in the urine and plasma of patients treated with radiation, to compare the levels detected with each method, to determine if one method is superior, and to determine if levels of TGF β 1 correlate with chronic gastrointestinal toxicity. TGF β 1 levels will be determined in platelet poor plasma.

- Leukocyte markers

Other possible markers of early and late gastrointestinal toxicity are markers of intestinal inflammation. Without biopsies of irradiated tissues, direct evidence of inflammation in the intestinal wall is unavailable; however numerous indirect measures of intestinal inflammation are available. Neutrophil elastase is known to be secreted from activated neutrophils and has been implicated in endothelial cell and epithelial cell apoptosis⁴⁹. Importantly, endothelial cell apoptosis and microvascular dysfunction have been implicated in radiation induced clonogen depletion in the intestine⁵⁰. In addition, neutrophil elastase has been implicated in epithelial injury⁵¹ and inflammatory diseases of the intestines⁵²⁻⁵⁴. This acute inflammation may play a role in the initiation of ongoing bowel inflammation and injury that is the hallmark of late GI toxicity. In pre-clinical models, several markers of neutrophil transmigration have been found to correlate with histologic markers of acute and chronic radiation enteropathy⁵⁵. Fecal lactoferrin has been shown to correlate with histologic evidence of bowel inflammation^{56, 57}. We will determine the clinical utility of fecal and serum elastase, fecal calprotectin, and fecal lactoferrin as markers of neutrophil transmigration and surrogate markers of acute and chronic bowel injury.

- Extracellular matrix proteins

Evaluations of gene expression in chronic radiation enteropathy have reported an increase in transcripts related to extracellular matrix (ECM) remodeling and fibrosis⁵⁸⁻⁶¹, consistent with the pathologic findings of fibrosis described in clinical series⁴⁰. Altered collagen subtype ratios have been reported in intestinal injury to be mediated by TGF β , which is thought to play a major role in the pathogenesis of chronic bowel injury due to radiation⁴⁰.

Collagen type I and III are synthesized as procollagen precursors that must be cleaved to form collagen. Measurements of serum pro-peptide levels, such as the carboxy-terminal propeptide of procollagen type I (PICP) and the amino-terminal propeptide of collagen Type III (PIIINP) provide a measure of collagen deposition and have been evaluated in a variety of disease states linked to fibrosis⁶²⁻⁷². In addition, the amount of cross-linked carboxy-terminal telopeptide (CITP) is proportional to the amount of collagen degradation and together with PICP and PIIINP may provide markers of the collagen turnover that occurs with fibrosis⁷³.

Preclinical models of radiation induced bowel fibrosis have confirmed increased deposition of Type I and Type III collagen in the bowel wall detected by immunohistochemistry³⁸. In patients, altered collagen deposition has been evaluated in radiation injury of the skin⁷⁴⁻⁷⁶ and in patients with radiation induced pulmonary fibrosis^{77, 78}. The measurement of serum markers of collagen deposition and turnover through measurement of pro-collagen peptides provides a non-invasive method of evaluating ongoing extracellular matrix remodeling and fibrosis.

The utility of these markers of fibrosis in the setting of radiation toxicity will be evaluated in patients who undergo radiotherapy. The timing of any surgery or biopsies, if performed, will be recorded as this may be a factor that alters the utility of these measures as markers of for ongoing fibrosis. It is likely that the ongoing chronic inflammation and fibrosis characteristic of the late toxicity of radiation will have a different time course of expression of these molecules than that induced by surgery. While elevated procollagen peptides have been reported in the serum of patients with widespread metastatic bony disease⁷⁹⁻⁸², this should not be a confounding factor except in patients who develop this complication. Special attention will be paid to the symptoms or radiographic evidence of the development of bone metastases during the follow-up period.

- *Functional measures of intestinal injury*

Intestinal absorption of lipids, monosaccharides, and polysaccharides has been used to evaluate small intestine function in various disease states. Alterations in the bowel wall due to denudation, edema, barrier function, and fibrosis may affect intestinal absorption. Alterations in barrier saccharide absorption have been noted in radiation patients²⁸ but this has

not been correlated to clinical symptoms of radiation enteropathy. Acute radiotherapy induced acute intestinal malabsorption may correlate with the degree of bowel injury and eventually the likelihood of developing chronic intestinal toxicity. One test that has been used to evaluate changes in intestinal absorption during radiotherapy is a comparison of the transport of monosaccharides to disaccharides across the intestinal wall, which is commonly known as an intestinal permeability test⁸³. This has yet to be evaluated as a correlate of late toxicity.

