3.0 STUDY IMPLEMENTATION

3.1 STUDY DESIGN

3.1.1 Overall Trial Design (see Appendix IA)

Patients planned to receive radiotherapy for carcinoma of the esophagus, stomach, pancreas, rectum, or other biliary malignancies as part of their primary therapy will be potential candidates for enrollment on this protocol. This is not a study of an experimental therapy and will be administered in conjunction with protocol therapy for patients receiving radiation as part of the treatment of a gastrointestinal carcinoma. 120 patients will be included from the following sites: 30 patients with esophageal or GE junction cancer, 30 patients with locally advanced biliary malignancies (including pancreas and bile ducts only), 30 patients with resected biliary malignancies (including pancreas and bile ducts only), and 30 patients with rectal cancer.

Serum, plasma, urine, and stool samples will be collected prior to any therapy (surgery excluding biopsy, systemic therapy, or radiotherapy), prior to radiotherapy (if different from "prior to any therapy"), at completion of radiation (within the final five fractions), and at 1, 3, 6, 12, 24, and 36 months follow-up

The Intestinal Permeability Assessment will be performed following protocol sample collection (above) at the following time points: prior to any therapy, prior to radiotherapy (if different than "prior to therapy"), at 1 month follow-up, and at 3 months follow- up.

Tumor tissue obtained at biopsy or resection will be screened for a defined panel of mutations using PCR and abnormal methylation status will be determined by methylation specific PCR. Serum, urine, and stool samples obtained prior to therapeutic intervention will be screened for the same panel of markers. Serum, urine, and stool obtained during treatment and at follow-up will be evaluated for these

same DNA markers and correlated to evidence of gross residual disease on physical examination and follow-up imaging.

Potential serum, plasma, and stool markers of gastrointestinal toxicity will be correlated to validated measures of gastrointestinal toxicity.

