3.5 RADIATION THERAPY GUIDELINES

This is not a study of an experimental therapy. It is to be performed in conjunction with protocol therapy for patients receiving radiation as part of a primary treatment of carcinoma of the esophagus, stomach, bile ducts, pancreas, or rectum.

Radiation dose to various intraabdominal structures will be calculated and recorded. The organs contoured will vary for each site; however, typically this will include the stomach, small bowel, duodenum (contoured separately from the remainder of the small bowel), liver, colon, rectum, bladder, kidney, heart, lung, and esophagus. If any of these organs is included in any radiation field it will be contoured in its entirety on the CT simulation planning image set and the minimum, maximum, mean, and median dose to this organ will be recorded. In addition, the percentage and volume of this organ receiving above the accepted tolerance dose will be recorded.

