For the first primary objective, tumor-specific DNA mutation markers will be collected at baseline (before any therapy and before radiation begins) at completion of radiation therapy and at 1, 3, 6, 12, 24, and 36 months of follow-up. Of interest is examining whether changes in the average mutation frequency (of the disease-specific mutations given in Appendix IIA) effects response to therapy, overall survival, and disease-free survival among complete responders to all therapy. Various analyses will be done to address with objective. These analyses will be done separately by tumor type as well as combined over tumor type (assuming that the relationship between marker changes and disease outcome do not vary across tumor type). First, we will examine the relationship between changes in mutational status over time and survival with Cox proportional hazards models. The relationship between changes in mutational status over time and complete response will be estimated using logistic regression analysis. One key primary analysis will be to examine whether having all tumor-specific markers being negative at 3 months after radiation therapy ends is associated with long-term survival. Note that based on the tumor marker prevalences in the literature (see Appendix IIC) and an assumption that marker prevalence is independent across the various markers, the probability of having at least one mutation which is positive before treatment is very high. Our sample size calculations assume that 50% of patients will have all tumor-specific markers negative 3 months after radiation therapy ends. Based on conducting a two-sided log-rank test at the 0.05 significance level with a total enrollment of 120 patients, we would have 89% power to detect a difference between 35% overall 2-year survival in the positive marker group and 65% overall 2-year survival in the negative marker group. We will have power only to detect large differences for the tumor-specific analyses. With 30 patients in each group (15 patients in the positive and negative groups, respectively), we would have 83% power to detect a difference in 2 year survival of between 80% in the marker negative group and 20% in the marker positive group using a log-rank test at the 0.05 significance level. The above sample size calculation depends heavily on the assumption that 50% of patients will have all tumor-specific markers negative at 3 months. The power may be severely diminished if this proportion deviates too much from 50%. Thus, alternative similar analyses will also be conducted. For example, we will compare survival by whether the change in tumor-specific marker frequency from

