5.4.2 Association between longitudinal measures of TGF β 1 and late gastrointestinal toxicity

We will examine whether levels of TGF β 1 measured in urine and plasma at various timepoints during and after therapy are associated with late gastrointestinal toxicity. Of particular interest will be examining whether changes in TGF β 1 measured over time affect the probability of RTOG ≥ 2 toxicity at 12 months after the completion of radiation therapy. The analysis will be done by relating change in TGF β 1, evaluated by estimating a slope using least-squares regression on each patients repeated follow-up measurements, and the probability of RTOG ≥ 2 at 12 months after completion of therapy using logistic regression. These analyses will be done with and without adjustment for radiation dose to non-target organs (radiation dosimetry). Interest will focus on whether a positive change in TGF β 1 over time (positive slope) is associated with an RTOG ≥ 2 toxicity at 12 months post-therapy. We expect that, on average, approximately 60% of patients will have a RTOG ≥ 2 at 12 months. We also assume that at a minimum of 76 patients of 120 accrued to the study will be alive at 12 months (there is a 95% chance that there will be 76 or more patients will be alive and evaluable at 12 months if the one-year survival/evaluable rate is 70%). Assuming a that 76 patients will be evaluated for toxicity at 12 months and that 50% of estimated slopes are positive, we will have 93% power to detect a difference in the proportion of RTOG ≥ 2 at 12 months of 80% for a positive slope as compared with 40% for a negative or zero slope with a Chi-square test at the 0.05 significance level. A logistic regression analysis treating the estimated slope as a continuous variable should have more power than the Chi-square test.

5.4.3

Analysis of secondary objectives

We will compare the accuracy of DNA mutations and DNA methylation tests in serum, urine, and stool (relative to tumor biopsy) by comparing estimated sensitivities and specificities of the various tests.

We will evaluate which biological fluid provides the best source of tumor specific DNA for association with subsequent disease using logistic regression and Cox proportional hazards models with DNA tests from the different fluids being independent variables in the models.

We will relate novel serum, urine, and stool markers measured during and shortly after treatment to toxicity using logistic regression analysis similar to 5.3.2.

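### Section 5.4.2 pools esophageal patients into the TGFβ1 and late-toxicity test without allowing for tumor site, so site can confound or dilute a primary result

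*Combined protocol and SAP*

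**What the plan says.** Section 1.2.3.2 presents TGFβ1 as a candidate marker of intestinal injury. The clinical evidence it cites for plasma is from patients irradiated for lung cancer, in whom TGFβ1 "levels correlated with radiation induced pneumonitis".

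Section 3.1.1 plans 120 patients in four groups of 30, one of them "30 patients with esophageal or GE junction cancer". Section 3.5 includes "kidney, heart, lung, and esophagus" among the organs typically contoured and adds: "If any of these organs is included in any radiation field it will be contoured in its entirety". Dose summaries are then recorded for that organ.

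Section 5.4.2 fits a slope to each patient's TGFβ1 values and relates it to RTOG ≥2 toxicity at 12 months: "Interest will focus on whether a positive change in TGF"β1 goes with that outcome. The test is sized on 76 evaluable patients from all sites together: 80% toxicity with a positive slope against 40% otherwise, half the slopes positive, 93% power. On covariates it says: "These analyses will be done with and without adjustment for radiation dose to non-target organs (radiation dosimetry").

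For the DNA markers, section 5.4.1 says: "These analyses will be done separately by tumor type as well as combined over tumor type". Section 5.4.2 has no matching sentence. The late-toxicity form (Appendix IIIB) has rows for esophagus, intestine and liver.

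**The concern.** Esophageal and GE junction patients may differ from the abdominal and pelvic groups in two ways that matter here. Lung in the field could raise plasma TGFβ1 for reasons unrelated to the gut. They can also reach late grade 2 through swallowing criteria rather than bowel criteria, and so perhaps at a different rate.

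If only the slope is affected, and without relation to GI toxicity, the pooled contrast is weakened. If slope and toxicity rate both differ by site, tumor site confounds the pooled test and can produce an association, in either direction, that exists within no site. TGFβ1 as a predictor of late GI toxicity is a primary objective, and urine and plasma are both part of it. The lung evidence cited concerns plasma only. Confounding by site could affect either fluid.

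**Working it through.** **Inputs.** From section 5.4.2: 76 evaluable, 50% positive slopes (38 v 38), 80% v 40% toxicity, overall toxicity 60%, chi-square at 0.05. From section 3.1.1: 30 of 120 esophageal. Assumed: equal evaluability across sites, giving 76 × 30/120 = 19 esophageal and 57 other patients. The documents give no site-specific slope or toxicity rates, so those below are also assumptions.

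**1. The plan's own figure.** With n = 38 per group, d = 0.40 and mean rate 0.60, continuity-corrected power is Φ[(d − 1/n − 1.96·√(2·0.6·0.4/n)) / √((0.8·0.2 + 0.4·0.6)/n)] = Φ[(0.400 − 0.026 − 0.220)/0.103] ≈ 93.3%. Exact enumeration gives 92.9% corrected and 95.8% uncorrected. The stated 93% reproduces with the correction, so there is no arithmetic error.

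**2. Dilution.** Let slope sign carry no information in the 19 (60% toxicity either way) while the other 57 follow the plan:
- positive slope: 0.75 × 0.80 + 0.25 × 0.60 = 75%
- other slope: 0.75 × 0.40 + 0.25 × 0.60 = 45%

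Exact power at 38 v 38 is then 68.9% corrected (77.2% uncorrected). The 57 alone (29 v 28 at 80% v 40%) give 85.1% (90.7%). The corrected normal approximation for the 57 is lower, at 82.5%.

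In a graded version, lung injury turns a share f of the non-positive esophageal slopes positive regardless of GI toxicity. Power by the corrected normal approximation:

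| f | 0 | 0.25 | 0.5 | 0.75 | 1 |
|---|---|---|---|---|---|
| Power | 93.3% | 89.1% | 84.0% | 78.1% | 71.6% |

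**3. Confounding, with no association within any site.** In the strong scenario, positive slopes are 80% in esophageal patients v 40% in the others, and toxicity is 80% v 53.3%. The totals still match the plan: (19 × 0.8 + 57 × 0.4)/76 = 50% positive slopes and (19 × 0.8 + 57 × 0.533)/76 = 60% toxicity. Pooling creates a contrast:
- positive slope: (15.2 × 0.8 + 22.8 × 0.533)/38 = 64%
- other slope: (3.8 × 0.8 + 34.2 × 0.533)/38 = 56%

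Simulated rejection rates:

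| Scenario | Pooled, uncorrected | Pooled, corrected | Stratified (Mantel-Haenszel), uncorrected |
|---|---|---|---|
| Strong: slopes 80% v 40%, toxicity 80% v 53% | 11% | 7% | 5% |
| Milder: slopes 70% v 43%, toxicity 70% v 57% | 6% | 3% | 5% |

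A second set of scenarios keeps 50% positive slopes in the other sites and 75–100% in esophageal patients. Uncorrected pooled rejection is about 5% if esophageal toxicity is also 60%, 6–11% if it is 75%, and 11–28% if it is 90%. If it is 40%, rejection is 7–15%, almost all in the inverse direction. The stratified test stays at about 5% throughout.

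**4. What stratifying costs and recovers.** If the planned effect holds at every site, corrected power moves from 92.9% pooled to 92.4% stratified. In the dilution case of step 2 it is about 69% either way, so stratifying removes the confounding but does not restore diluted power.

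**The case against.** The strongest reply is that the plan already foresees the problem. Lung dose is recorded when the lung is in a field, and the TGFβ1 analyses are repeated with adjustment for non-target organ dose. Where the lung is outside every field, the lung mechanism largely falls away, so recording dose only for organs in a field is no real gap. This stands in part. Section 5.4.2 does not name the organs or dose measures, does not say whether the adjusted version is primary, and sizes the study on an unadjusted chi-square. Dose is also only a proxy for injury, and it does not capture a site difference in how toxicity is scored.

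A reader might infer that the study records no lung toxicity. The documents do not support that. Section 5.3.1 grades acute toxicities by CTC version 3.0 without limiting them to the gut, and section 3.3.3 requires a complete history and examination at each follow-up visit. What is absent is a planned late lung score: neither RTOG form has a lung row, and no lung data are linked to the TGFβ1 analysis.

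It is also fair to say that the site differences are invented, that the strong scenario needs a doubling of positive slopes together with a large toxicity difference, and that 69% requires the signal to vanish in all 19 patients. No passage says how many will have lung in the field. Finally, this is a pilot and TGFβ1 is a candidate marker. These points limit the size of the concern but do not justify a primary analysis that ignores a site variable already collected.

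**Conclusion.** The point holds as a design weakness in the primary TGFβ1 analysis: one pooled comparison, no site term, and a cited non-gut source of the plasma signal that may apply to a quarter of enrolment. Its size depends on assumptions the documents cannot settle. Confounding ranges from negligible under mild site differences to about 11% uncorrected (7% corrected) in the strong scenario, and higher only under more extreme inputs. Dilution ranges from a few points of power to a floor of 69%.

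A reader might go further and conclude that a lung-driven rise will be read as a gut signal. That does not follow. The outcome is observed RTOG ≥2 toxicity, so a rise unrelated to it mainly weakens the association. A false positive signal also requires a higher toxicity rate in esophageal patients, and a lower rate pushes toward an inverse association.

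**What to change.** In section 5.4.2:

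- Make the primary TGFβ1 analysis stratified by or adjusted for tumor site, using logistic regression with a site term or a Mantel-Haenszel test.
- Name lung dose among the dosimetry covariates.
- Report the plasma result for the non-esophageal groups as a sensitivity analysis. This, rather than stratification, addresses dilution.

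Site and dose are already collected, so the change is wording. If the planned effect holds at all sites, stratifying costs less than one percentage point of power, and the restricted analysis has about 85% rather than 93%.

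Two further steps are best avoided. Excluding patients with recorded lung toxicity conditions on a post-treatment outcome that may share causes with gut toxicity. Barring a GI-marker claim when the association appears only in esophageal patients would ignore that esophageal injury counts as GI toxicity on this protocol's own form.
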